7.2.14.2 Bone Marrow

At the screening visit, a uni- or bilateral bone marrow aspirate and a biopsy should be obtained to assess bone marrow involvement. Results from a bone marrow examination done within the 4 weeks prior to the date of informed consent will be acceptable if the patient's disease has been stable since then.

The achievement of CR in the course of MOR208C203 study must be confirmed locally, by clinical and radiologic evaluation along with bone marrow confirmation. The latter applies only in case the bone marrow was involved by lymphoma before study entry. If bone marrow was not involved by lymphoma before commencing the study treatment, then bone marrow confirmation biopsy is not required. The repeated bone marrow examination is also not required for patients in whom bone marrow has already been cleared of the infiltrate at previous evaluation, i.e. their previous response was CR.

Histological examination of the bone marrow should be performed locally at the protocol specified time-points (see [Table 5](#)).

8 SAFETY MONITORING

The patients will be closely observed and questioned for any kind of AE during the study procedures and at follow-up appointments throughout the study period with non-leading questioning (e.g., "How do you feel?"). AEs also may be detected when they are volunteered by the patient during or between study visits or through physical examination, laboratory tests, or other assessments.

Study personnel must remain vigilant for the occurrence of AEs, particularly those that may be lifethreatening-. Personnel who are trained in the acute management of IRRs, cytokine release syndrome, anaphylaxis, and other emergencies, and who have access to appropriate clinical supplies, should be readily available.

All AEs should be treated appropriately. Such treatment may include changes in study drug treatment including possible interruption or discontinuation, starting or stopping concomitant treatments, changes in the frequency or nature of assessments, hospitalisation, or any other medically required intervention. Once an AE is detected, it should be followed up, and an assessment should be made at each visit (or more frequently, if necessary) of any changes in its severity, its suspected relationship to the study drug(s), any of the interventions required to treat it, and its outcome.

8.1 Definition of Adverse Events, Serious Adverse Events, Adverse Events of Special Interest

An AE is defined as any untoward medical occurrence in a patient or clinical patient administered a medicinal product, which does not necessarily have a causal relationship to this treatment.

An AE can therefore be any unfavourable and unintended sign (including an abnormal laboratory finding), symptom, or disease temporally associated with the use of a study drug, whether or not it is considered related to that study drug.

AEs include any clinically significant deterioration of a patient's medical status after the signing of the ICF. Also, an increase in the frequency or intensity of a pre-existing episodic event or conditions and events resulting from protocol mandated procedures (e.g., invasive procedures) fall under the definition of AEs. In addition, overdoses (defined as exceeding the planned dose by more than 20%) should be recorded as AEs.

As far as possible, each AE should be evaluated to determine the following:

- relationship to the study drug (suspected/not suspected)
- duration (start and end date or if continuing at end of study)
- intensity: the intensity of all AEs will be graded as mild, moderate, or severe using the following definitions:
 - mild: tolerable
 - moderate: interferes with normal activity
 - severe: incapacitating (causes inability to perform usual activities or work)
- toxicity grade: determined according to the NCI-CTCAE version 4.0 of May 28, 2009, using the following definitions:
 - grade 1: mild; asymptomatic or mild symptoms; clinical or diagnostic observations only; intervention not indicated
 - grade 2: moderate; minimal, local or noninvasive intervention indicated; limiting age-appropriate instrumental activities of daily living (refers to preparing meals, shopping for groceries or clothes, using the telephone, managing money, etc.)
 - grade 3: severe or medically significant but not immediately life-threatening; hospitalisation or prolongation of hospitalisation indicated; disabling; limiting self-care activities of daily living
 - grade 4: life-threatening consequences; urgent intervention indicated
 - grade 5: death related to AE
- outcome
- action taken (no action taken; study drug temporarily interrupted; study drug permanently discontinued due to this AE; concomitant medication taken; non-drug therapy given; hospitalisation/prolonged hospitalisation)
- seriousness: whether it is serious, where a SAE is defined as one that:
 - results in death
 - is life-threatening
 - requires inpatient hospitalisation or prolongation of existing hospitalisation (hospitalisation signifies that the patient was an inpatient for at least one overnight stay) unless hospitalisation is for:
 - routine treatment or monitoring of the studied indication, not associated with deterioration of symptoms related to NHL
 - elective or preplanned treatment for a pre-existing condition that is unrelated to NHL and has not worsened since signing of the informed consent
 - social reason and respite care in the absence of any deterioration in the patient's general condition
 - hospitalisation signifies that the patient was an inpatient for at least one overnight stay
 - results in persistent or significant disability or incapacity
 - is a congenital anomaly or birth defect
 - is medically significant, i.e. defined as an event that jeopardises the patient or may require medical intervention to prevent one of the outcomes listed previously.

The term “life-threatening” refers to an event in which the patient was, in the view of the reporting investigator, at immediate risk of death at the time of the event; it does not refer to an event that hypothetically might have caused death if it were more severe. Medical judgment should be exercised in deciding whether an AE is serious in other situations: important AEs that are not immediately lifethreatening- or do not result in death or hospitalisation but may jeopardise the patient or may require intervention to prevent one of the other outcomes listed in the previous definitions should also be considered as serious.

AEs of special interest are TFR, TLS, SPM, IRRs and allergic reactions to study drug \geq grade 3, cytokine release syndrome and overdoses.

Unlike routine safety assessments, SAEs and AEs of special interest are monitored continuously and have special reporting requirements (see [Section 8.2](#)).

The investigator should determine the causality (relationship to the study drugs) based on his/her clinical experience and on the information given in the IB for MOR00208 and the SmPC / Prescribing Information for lenalidomide. The causal relationship of all AEs to the study drug will be judged as either suspected or not suspected. A suspected causal relationship means at least a reasonable possibility that the event is caused by the study drug. If no relationship has been provided by the investigator, the event will be considered as related to the study drug.

Information about adverse drug reactions already known about the investigational study drugs can be found in the IB for MOR00208 and the SmPC from lenalidomide, or will be communicated in the form of Investigator Notifications. This information will be included in the patient ICF and should be discussed with the patient during the study, as needed.

8.2 Adverse Event and Serious Adverse Event Recording and Reporting

All AEs (except non-serious AEs for screening failures) that occur after the provision of informed consent and up to 30 days after last study drug administration will be recorded in the eCRF and in the patient’s medical records, whether or not they are considered by the investigator to be related to the study drug. Thereafter, only AEs assessed as related should be recorded. All AEs should be recorded using acceptable diagnoses, if possible. For screening failure patients, non-serious AEs will not be recorded in the eCRF but only in the patient’s medical records.

In addition, all SAEs and AEs of special interest will be recorded on the SAE report form. Study centres and investigators are instructed to report all SAEs and AEs of special interest to the contract research organisation (CRO) mentioned below within 24 hours using the study-specific- SAE report form. Preferably, the diagnosis instead of the individual symptoms should be reported. For overdoses, the diagnosis and if applicable the accompanying symptoms caused by the overdose should be reported.

If an AE has already been reported, it is not necessary to report each individual sign and symptom of that AE as a separate AE. For example, if a myocardial infarction is reported as an AE, there is no need to report elevated creatine phosphokinase and abnormal ECG, or other related signs,

symptoms, or laboratory values as separate AEs. However, if such events occur in isolation, and myocardial infarction is not diagnosed, then each event should be reported as an AE.

[figure not shown]
All non-serious AEs must be followed up for a final outcome. An outcome of “unknown” is not considered to be an acceptable final outcome. An outcome of “not yet resolved” is an acceptable final outcome for non-serious AEs at the end of a patient’s participation in a study. All SAEs must be followed up for a final outcome until resolution or, if resolution becomes unlikely, until stabilisation or death. The follow-up for SAEs that are a progression of DLBCL only until the end of a patient’s participation in a study is acceptable. This includes obtaining information on recovery and any sequelae and, in the case of a fatal outcome, the cause of death.

Events that are clearly caused by progression of the underlying disease (for example transformation to more aggressive histology) should not be recorded as AEs or SAEs. These data will be captured as efficacy assessment data only. If there is any uncertainty as to whether an event is due to disease progression, it should be recorded as an adverse event.

Deaths that occur during the protocol-specified adverse event reporting period that are being attributed to progression of the underlying disease should not be recorded as AEs or SAEs. All other on-study deaths, regardless of relationship to study drug, must be recorded on the Adverse Event eCRF and immediately reported to the Sponsor. Death should be considered an outcome and not a distinct event. The event or condition that caused the fatal outcome should be recorded as the single medical concept on the Adverse Event eCRF. Generally, only one such event should be reported.

During survival follow-up, deaths attributed to progression of the underlying disease should be recorded in the eCRF.

Notification of initial or followup- SAE information (by using the standard SAE form provided by the sponsor) must be sent by fax to the CRO at the following numbers as appropriate:

[figure not shown]

For any safetyrelated- or protocol related questions, please use the contact numbers below (24/7 coverage):

24/7 Medical Emergency Coverage (out of office hours)	
Medical Emergency Coverage (during Medical Monitor office hours)	

8.3 Pregnancies

As detailed in the Schedule of Assessments (Table 5) and Section 7.1, serum pregnancy testing will be carried out at the Screening, and End of Treatment Visits (performed centrally). During the treatment period of the study, urine pregnancy testing will be performed locally and can be repeated if required. Any pregnancy that occurs during study participation should be reported using a Clinical Trial Pregnancy Form. To ensure patient safety, each pregnancy of a study patient or a female partner of a study patient must also be reported within 24 hours of learning of its occurrence to [REDACTED] by fax at the following number:

Female study patients who become pregnant must be withdrawn from the study treatment period (IMP is to be discontinued immediately).

A newly diagnosed pregnancy in a patient or female partner of a study patient who has received study medication is not considered an SAE unless it meets any criteria of seriousness or it is suspected that the study medication interacted with a contraceptive method and led to pregnancy.

If the pregnancy results in clinical consequences/complications in mother or child, e.g., if the child is born with a birth defect, this should be reported as an SAE of mother or child as applicable.

The pregnancy should be followed up to determine outcome, including spontaneous or voluntary termination, details of birth, and the presence or absence of any birth defects or congenital abnormalities or maternal and newborn complications. Every infant has to be followed up for 2 months after delivery.

9 DATA HANDLING AND ARCHIVING

9.1 Completing and Signing Case Report Forms

Electronic CRFs will be used in this study. Data will be entered by trained site personnel, with reasons given for any missing data. Any errors should be corrected within the electronic system. The audit trail will record all changes made, the date and time of the correction, and the person correcting the error. The appropriate electronic signature will be provided. The investigator will receive a copy of their eCRF in a readable format after database lock for archiving.

9.2 Clinical Data Management

The CRO will be responsible for the processing and quality control of the data according to the CRO's standard operating procedures (SOPs). Data management will be carried out by the CRO. The handling of data, including data quality control, will comply with all applicable regulatory guidelines.

Details for data validation and edit checks will be described in appropriate data management documents. Queries will be handled via the eCRF system. Data cleaning will continue until all queries are resolved.

Medical coding will use Medical Dictionary for Regulatory Activities (MedDRA, Version 18.0 or higher) for AEs and medical history and the WHO-drug dictionary enhanced for medication.

9.3 Archiving and Filing

All study documentation at the investigator site and sponsor site will be archived in accordance with International Conference on Harmonisation (ICH) E6 Good Clinical Practice (GCP) guidance and the clinical trial agreement.

10 STATISTICAL METHODS AND PLANNED ANALYSIS

10.1 Populations for Analysis

The following analysis populations will be used:

- **Full analysis set (FAS):**
The FAS includes all patients who received at least one dose of MOR00208 and one dose of LEN. This means that both study drugs must have been applied at least once.
- **Per protocol set (PPS):**
The PPS is the subset of all subjects in the FAS without any major protocol non-compliances. All patients in the FAS, had at least one dose of MOR00208 and one dose of LEN drug. Patients without any post-baseline assessment of DLBCL response or having major protocol deviations will be excluded from the PPS.
- **Safety analysis set (SAF):**
All patients who received at least one dose of MOR00208 or LEN study drug.

Primary, secondary and supportive efficacy parameters will be evaluated using the FAS and PPS, while safety parameter evaluations will use the safety set (SAF), as well as for evaluations on immunogenicity and biomarkers.

The primary analysis of the primary efficacy endpoint will be based on the FAS, whereas the analysis using the PPS has a supportive function. Decisions about whether a protocol deviation is relevant for the exclusion of a patient from the PPS will be made before database closure.

10.2 Primary Endpoint

1. The primary efficacy endpoint will be ORR (ORR = CR + PR)

10.3 Secondary Endpoints

2. DCR, DoR, PFS, OS, TTP and TTNT
3. Incidence and severity of AEs
4. Determination and characterisation of a potential anti-MOR00208 antibody formation
5. PK analysis of MOR00208
6. Absolute and percentage change from baseline in measurements of B-, T- and NK cell populations
7. Analysis of exploratory and diagnostic biomarkers (e.g., CD19, CD20, BCL2, and BCL6 expression, CD16 expression on NK cells, ADCC capacity, and gene expression profiling for cell of origin subtyping and evaluation of AEs and ORR stratified by Fc γ RIIIa and Fc γ RIIa polymorphism) are planned to be investigated during the course of the study.

10.4 General Statistical Methods

Tabulation of summary statistics, graphical presentations, and statistical analyses will be performed using appropriate statistical software. Continuous, quantitative variable summaries

will include the number of patients (N) (with non-missing values/valid cases), mean, standard deviation, minimum, 25th quartile, median, 75th quartile and maximum, except for pharmacokinetic metrics, where additional statistics may be used.

Categorical, qualitative variable summaries will include the frequency and percentage of patients/entries, who/which are in the particular category.

The assumed overall type I error rate/significance level for the primary and secondary efficacy parameters is 5%, two-sided. Two-sided confidence limits will be evaluated at 95%, p-values from inferential tests comparing specific patient cohorts/patient subgroups will be compared to 5%.

Missing values will not be substituted by estimated values. All statistical evaluations will be based on valid cases except for procedures described for calculating response rates or in case of censoring within the Kaplan-Meier methodology. In the case of incomplete start or stop dates of AEs or concomitant medication appropriate conservative imputation methods will be specified in the Statistical Analysis Plan (SAP).

Baseline values will be defined as the last pre-administration observation used for calculating post-administration changes from baseline.

All data obtained and entered into the database will be provided in separate data listings showing individual patient values. A SAP detailing the statistical analyses and possible deviations from the protocol will be prepared before hard lock of database.

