10.8 Sample Size Determination

Approximately 80 patients with R-R DLBCL who meet the inclusion criteria and have none of the exclusion criteria will be randomly enrolled into the study. The study will be performed with an interim stop for the evaluation of the safety of the LEN dosage. No adjustment of sample size

or adaptation of efficacy evaluations will be made at this point. As the primary purpose of this study is to evaluate the clinical efficacy of 25 mg daily oral LEN combined with 12 mg/kg MOR00208 administered by IV infusion in patients with R-R DLBCL, no formal statistical hypothesis testing will be performed.

For the determination of a suitable sample size, it is assumed that the combination treatment could improve the ORR from a value of 20% (under monotherapy) to 35% (under combination therapy). Applying an exact binomial test with a two-sided significance level of 5% and a power of 85% the estimated sample size is 73 patients (calculation performed by nQuery Advisor® 7.0). According to this scenario an observed ORR of 32% would lead to a statistically significant study outcome. Assuming a drop-out rate of 10%, a total sample size of about 80 patients is estimated.

The sample size determination has been conducted using various possible monotherapy and combination effect ORR rates and various power assumptions. Literature evaluation of study results concerning the ORR rates of LEN or comparable products (as mono- or combination-therapy) as well as former study results for MOR00208 were used to justify assumptions on response rates ([Witzig et al., 2011](#); [Wang et al., 2013](#)).

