10.12.2 Endpoint

PFS, DoR, ORR, OS will be analyzed in the following subgroups:

- FcγRIIIa affinity (high affinity: FCGR3A-158V homozygosity vs. low affinity: FCGR3A-158F homozygosity, or FCGR3A-158F/V heterozygosity).
- FcγRIIIa affinity (high affinity: FCGR2A-131H homozygosity vs. low affinity: FCGR2A-131R homozygosity, or FCGR2A-131H/R heterozygosity).
- Peripheral NK cell numbers at baseline (< median of NK cell numbers/μl vs. >= median of NK cell numbers/μl).
- Cell of origin determined by immuno-histochemistry (IHC) (i.e., central pathology) assessment: germinal center B cell (GCB) phenotype vs. non-GCB phenotype.
- Cell of origin determined by gene expression profiling (GEP): GCB phenotype vs. activated B cell (ABC) phenotype vs. unclassified phenotype.

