10.12.3 Main analysis

The following analyses will be conducted on the FAS:

- The main analyses pertaining to the biomarker subgroup analyses are being described in the respective sections above addressing ORR, PFS, DoR, and OS (Sections 9.2, 10.1.3, 10.2.5, 10.3.4, and 10.4.4).
- PFS, DoR and OS will be compared between subgroups by a log-rank test.
- For PFS and OS analyses, the estimate of the hazard ratio and corresponding 95% CI will be calculated using a Cox proportional hazards model with only one covariate (i.e., the biomarker in question) in the model.

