10.12.4 Sensitivity analyses

The main analysis as described in Section 10.12.3 will be conducted based on the INV response assessment using the FAS.

A comprehensive analysis of all biomarker assessments will be described in a separate biomarker-specific Statistical Analysis Plan, and summarized in a separate report.

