16.5.8 NK cell numbers at baseline

In analogy to the subgroup analysis specified in Section 10.12 the NK cell categories are additionally defined using a cut-off of 100 NK cells/ μ l (<100 cells/ μ l vs. \geq 100 cells/ μ l). The following efficacy analyses will be conducted based on the FAS:

- PFS (based on IRC only)
- OS
- ORR (based on IRC only)
- DoR (based on IRC only)

Kaplan-Meier curves will be produced for time-to-event endpoints.

Baseline characteristics in the NK count subgroups defined by the cut-off of 100 NK cells/ μ l will be tabulated as described in Section 8.5.

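### The protocol's overall 5% type I error does not hold for the 15 unadjusted biomarker log-rank tests of secondary objective 12, so their p-values should be called nominal

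*Protocol*

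**What the plan says.** Protocol 10.4 sets the error rate: "The assumed overall type I error rate/significance level for the primary and secondary efficacy parameters is 5%, two-sided". The sentence after it sets the confidence level at 95% and adds that "p-values from inferential tests comparing specific patient cohorts/patient subgroups will be compared to 5"%.

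SAP 10.12 implements secondary objective 12, which relates efficacy to biomarkers. Section 10.12.2 lists five groupings: FcγRIIIa affinity, FcγRIIa affinity, baseline NK count split at the median, cell of origin by immunohistochemistry, and a fifth, "Cell of origin determined by gene expression profiling (GEP): GCB phenotype vs. activated B cell (ABC) phenotype vs. unclassified phenotype". SAP Table 1 lists only the first four for the same objective. Section 10.12.3 states that "PFS, DoR and OS will be compared between subgroups by a log-rank test". It names no test for ORR. Section 10.12.4 adds a repeat: "The main analysis as described in Section 10.12.3 will be conducted based on the INV response assessment using the FAS". Addendum section 16.5.8 brings in a second NK split: "In analogy to the subgroup analysis specified in Section 10.12 the NK cell categories are additionally defined using a cut-off of 100 NK cells"/µl.

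Neither document gives a testing hierarchy, an alpha split or an adjusted threshold for these comparisons. Both disclaim formal testing. Protocol 10.8 says that "no formal statistical hypothesis testing will be performed", SAP 5.3 agrees, and SAP 9.2 repeats the point for the main ORR analysis.

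**The concern.** An overall error rate is a statement about a whole set of tests. A rule that judges each p-value against 5% controls the error of one test at a time. With more than one test, the two statements in Protocol 10.4 cannot both be true.

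This matters most in SAP 10.12.3, which prescribes log-rank tests on secondary efficacy endpoints under a numbered secondary objective. The study has about 80 patients and DoR is defined only in responders, so several subgroups will be small and chance differences will be common. The report could call a biomarker predictive of PFS at p below 0.05, and a reader holding the protocol would take that result to sit under an overall error of 5%.

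**Working it through.** **Inputs from the documents**
- Stated overall error: 5%, two-sided (Protocol 10.4).
- Threshold per subgroup test: 5% (Protocol 10.4).
- Endpoints tested: 3, namely PFS, DoR and OS (SAP 10.12.3).
- Groupings: 5 (SAP 10.12.2) or 4 (SAP Table 1).
- Adjustment: none found.

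**Count.** 5 × 3 = 15 tests, or 4 × 3 = 12. This takes the three-level gene-expression grouping as one overall test per endpoint.

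**The plan's own figure.** If no biomarker is related to outcome and the k tests are independent, the chance of at least one p below 0.05 is 1 − 0.95^k. For k = 1 this is 5.0%, so the stated rate is reproduced for a single test.

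**Independent tests**
- k = 12: 1 − 0.95^12 = 46.0%
- k = 15: 1 − 0.95^15 = 53.7%

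**Correlated tests.** PFS, DoR and OS overlap, and so do the two cell-of-origin methods. The documents give no correlations, so four sets were assumed and the log-rank statistics simulated as multivariate normal under the global null (200,000 draws). The gene-expression test was treated as 2-df and the other biomarkers as unrelated to each other.

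| Assumed correlation | PFS–OS | PFS–DoR | DoR–OS | Two cell-of-origin methods | 12 tests | 15 tests |
|---|---|---|---|---|---|---|
| Low | 0.30 | 0.40 | 0.20 | 0.40 | 44% | 51% |
| Middle | 0.60 | 0.50 | 0.40 | 0.60 | 41% | 48% |
| High | 0.80 | 0.70 | 0.60 | 0.70 | 37% | 42% |
| Very high | 0.95 | 0.93 | 0.92 | 0.90 | 27% | 31% |

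The 12-test column leaves out the gene-expression grouping, so the correlation between the cell-of-origin methods plays no part in it.

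**A floor that needs no endpoint correlation.** Suppose the three endpoints always gave the same answer and the two cell-of-origin methods counted as one marker. Four unrelated markers (an assumption) would still give 1 − 0.95^4 = 18.5%, nearly four times the stated 5%.

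**Threshold needed to hold 5% overall.** Bonferroni gives 0.05/15 = 0.0033 per test, or 0.05/12 = 0.0042.

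**The case against.** The strongest reply is that this is not a testing study. The protocol and SAP both disclaim formal hypothesis testing, the SAP repeats this for each main efficacy analysis, and its methods section 7.2 sets no significance level. Section 10.12.3 also refers back to sections that carry the disclaimer, and it already supplies hazard ratios with 95% intervals for PFS and OS. This stands as far as the primary result goes: no decision rule depends on a biomarker test. It does not settle the point, because 10.12.3 does not itself carry the disclaimer and does prescribe a test. Protocol 10.4 then supplies the 5% rule by which a reader would judge the result.

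A second reply is that the biomarker comparisons lie outside the 5% family. Protocol 10.3 lists efficacy parameters apart from exploratory and diagnostic biomarkers, and 10.4 deals with subgroup p-values in a separate clause. That reading is arguable. But the endpoints tested are the secondary efficacy endpoints, under a numbered secondary objective, and nothing in SAP 10.12 calls the p-values nominal.

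Third, SAP 10.12.4 sends the comprehensive biomarker analysis to a separate plan, which is not available here. It may handle multiplicity, but the tests counted above are prescribed in this SAP.

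A reader might also infer a larger family: 10 investigator-assessed repeats of PFS and DoR make 25, and three more for the 100 cells/µl split make 28, with 72% and 76% under independence. The documents do not support leading with those counts. The repeats are headed as sensitivity analyses and re-read the same hypotheses, and section 16.5.8 asks for Kaplan-Meier curves without naming a log-rank test.

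**Conclusion.** The overall 5% in Protocol 10.4 is a property that the plan does not have. For the 15 tests of SAP 10.12.3, the chance of at least one false positive is about 54% if they are independent and about 31 to 51% under the assumed correlations. On 12 tests the independent figure is 46%.

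These figures assume that no biomarker is related to outcome and that each log-rank test holds its 5% size, which small groups may not ensure. The correlations are assumptions, so no single value should be quoted as the trial's true error rate. What does not depend on them is that 5% is reproduced only for one test, or for tests so dependent that they amount to one.

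A reader might go further and infer that the main efficacy result is compromised. It is not: ORR is reported as an estimate with a 95% interval and no formal test, and nothing here alters either. This is a modest point about what the report may call significant.

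**What to change.** 1. **Protocol 10.4.** Delete the claim of an overall 5% error for primary and secondary parameters, and the instruction to compare subgroup p-values with 5%. State instead that the primary analysis is the IRC-assessed ORR on the FAS with its two-sided 95% interval, and that all other p-values and confidence intervals are nominal and not adjusted for multiplicity.
2. **SAP 10.12.3 and 10.12.4.** Label the log-rank p-values nominal and exploratory, and say that they will not be described as significant.
3. **If a biomarker claim is wanted.** Apply Holm across the 15 IRC/FAS tests of 10.12.3, with 0.0033 as the threshold for the smallest p-value. Keep the investigator-assessed repeats and the 100 cells/µl NK split outside the family. Bring SAP Table 1 and 10.12.2 into line first, so that the family is defined, and fix it before the results are known.

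The cost is a few sentences and a footnote on the biomarker tables. No estimate changes and no new data are needed. The one loss is that no biomarker result may be called significant at an unadjusted 5%.
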